4.7.1.1 Discontinuation from Study Drug

The Investigator must diligently review incoming safety data. In particular hematological or neurological abnormalities should be considered as a potential reason to withdraw a patient from further trial participation.

Subjects must be discontinued from study drug in case of:

- [REDACTED]
- [REDACTED]
- [REDACTED]

- Subject unable to continue to comply with study requirements

Subjects who discontinue study drug prematurely will be asked to return to the clinic for a study completion/Early Withdrawal visit as soon as possible (see Section 4.6.2.3) including detailed safety and efficacy assessments (see Schedule of Assessments, Appendix 1 and Appendix 2) and may undergo follow-up assessments (see Section 4.6.2.4). The primary reason for premature study drug discontinuation should be documented on the appropriate eCRF.

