5.2.2 Blood Pressure and ECG Monitoring

While the overview of available respective clinical experience does not indicate an effect of balovaptan on heart rate and blood pressure, hypothetically antagonism of V1a could result in a decrease in blood pressure and impairment of orthostatic function.

- Blood pressure and pulse rate in supine position and in context of orthostatic challenge testing will be monitored in this study in pediatric patients.

As a standard policy of clinical trials sponsored by Roche, and not because of any specific concern of balovaptan, the following stopping rule is implemented with respect to QTc:

- A confirmed value for QTcF above 500 ms or a change from baseline by more than 60 ms will result in drug discontinuation (to confirm the initial abnormal value the ECG should be repeated within 30 minutes).

[REDACTED]

[REDACTED]

[REDACTED]

[REDACTED]

[REDACTED]

[REDACTED]

[REDACTED]

[REDACTED]

[REDACTED]

[REDACTED]

[REDACTED]

[REDACTED]

[REDACTED]

[REDACTED]

[REDACTED]

[REDACTED]

[REDACTED]

[REDACTED]

[REDACTED]

[REDACTED]

[REDACTED]

[REDACTED]	[REDACTED]
[REDACTED]	[REDACTED]
[REDACTED]	[REDACTED]
[REDACTED]	[REDACTED]
[REDACTED]	[REDACTED]
[REDACTED]	[REDACTED]
[REDACTED]	[REDACTED]

[REDACTED]

[REDACTED]

[REDACTED]

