- 10 Vital signs will be done pre-dose and 3 hours post--dose. Additionally, orthostatic function will be assessed pre-dose and 3 hours post-dose at Week 30.
- 11 Planned as off-site/home visit and can be done by a nurse, however can also be performed as clinic visits.
- 12 Tanner staging will be done in patients 7 years and older, but not after menarche in female patients and not after voice break in male patients.
- 13 PK samples should be collected in those that withdraw from the study early as long as ≤7 days after last dose.
- 14 For children 5–11 years old, additional questions will be asked in context of Columbia-Suicide Severity Rating Scale (C-SSRS; see Section 4.6.1.12).
- 15 Patients will be asked additional questions after completion of the PedsQL.
- 16 Safety interview will occur either at site or during telephone visit and will follow semi-structured interview as listed in Appendix 8. It will include a check on compliance with body temperature monitoring.
- 17 If these hematology samples are required, visits must be conducted either at the site or by a home nurse if appropriate.

Appendix 10
Schedule of Assessments: Open-Label Extension from Weeks 52 to 76

	Site	Site	Site	FU (2 W)	FU (6 W)
Week	64 ²	76 ²	EW ²	78	88 ²
Day	449	533	NA		
Time window (days)	±2	±2	NA	±2	7
Study site visits	x	x	x		x
Informed consent					
Physical and neurological examination	x	x	x		x
Tanner staging ³					x
Anthropometric measurements	x	x	x		x
Vital signs		x	x		x
ECG-12 lead		x	x		x
Hematology	P	x	x	x	x
Full serum chemistry ⁵	P	x ⁶	x ⁶		x ⁶
Safety questions ¹	x	x	x	x	
Coagulation		x	x		
Urinalysis		x	x		x
Pregnancy test ⁴	x	x	x		x
Dispensing of study medication	x				
Administration of study medication	x	x	x		
PK blood samples		x	x ⁷		

Appendix 10

Schedule of Assessments: Open-Label Extension to Week 76 (cont.)

- 2 If necessary these clinic visits (Week 64, Week 76, Early Withdrawal Visit, and 6-week Follow-Up Visit) can be performed over 2 consecutive days; assessments at screening can be performed over the entire screening time window. After premature discontinuation, an Early Withdrawal Visit should be arranged as soon as possible (see also Section [4.7.1.1](#))
- 3 Tanner staging will be done in patients 7 years and older, but not after menarche in female patients and not after voice break in male patients.
- 4 Pregnancy tests will be performed in female patients after menarche only.

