- 5 See Section [4.6.1.7](#) and lab manual for more details about full serum chemistry.
- 6 At rescreening (substudy only), Week 76/Early Withdrawal Visit, and Follow-Up Visit (6 weeks), glycated hemoglobin (HbA1c), thyroid stimulating hormone (TSH), and free thyroxine (T4) will be assessed.
- 7 PK samples should be collected in those that withdraw from the study early.
- 8 For children 5–11 years old, additional questions will be asked in context of Columbia-Suicide Severity Rating Scale (C-SSRS; see Section [4.6.1.12](#)).
- 9 Patients will be asked additional questions after completion of the PedsQL.

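### Appendix 10 marks a study-drug dose at the open-label Early Withdrawal visit, which its own footnote 2 and Section 4.7.1.1 place after study drug has been stopped; the timing of that visit's PK sample is also unclear

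*Protocol*

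**What the plan says.** **Appendix 10 (open-label, Weeks 52 to 76).** The column header reads "Week 64 ² 76 ² EW ² 78 88 ²", that is, Week 64, Week 76, EW, and follow-up at 2 and 6 weeks. The dosing row reads "Administration of study medication x x x". The PK row reads "PK blood samples x x ⁷". Footnote 2 says of the EW visit: "After premature discontinuation, an Early Withdrawal Visit should be arranged as soon as possible". Footnote 7, on the EW sample, says: "PK samples should be collected in those that withdraw from the study early".

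**Section 4.7.1.1.** "Subjects who discontinue study drug prematurely will be asked to return to the clinic for a study completion/Early Withdrawal visit as soon as possible".

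**Section 5.2.2.** One mandatory stop is the QTc rule, where a confirmed value over the limit, or a "change from baseline by more than 60 ms will result in drug discontinuation".

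**Section 4.6.2.3.** Subjects who leave the study early also attend the EW visit.

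**Appendix 1 (double-blind).** The dosing row is blank at EW. Footnote 14 allows the EW PK sample at any time.

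**Appendix 9 (open-label, Weeks 24 to 52), footnote 13.** "PK samples should be collected in those that withdraw from the study early as long as ≤7 days after last dose".

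**Section 4.6.1.8.** One EW sample is taken, at no fixed time within the visit. Dosing times are to be entered for the day of sampling and the day before.

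**The concern.** A visit that follows the end of treatment should not carry an unexplained dosing mark. Section 4.6.2.2 tells sites to follow the schedules. It also describes subjects arriving undosed at study visits and taking their dose there. A site reading that section together with Appendix 10 has a written basis for dosing someone whose treatment has already been stopped, possibly for safety.

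Two things are at stake in the data. The first is the last-dose date, which anchors the follow-up visits (Section 4.6.2.4) and the adverse-event reporting period (Section 5.3.1). The second is the EW PK sample, which can be interpreted only if its time since the last dose is known.

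**Working it through.** The plan gives no figure to reproduce here. The check sets the passages side by side; the arithmetic in steps 3 and 5 is illustrative.

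**Step 1. Is the EW mark a column shift?** Appendix 10 has five visit columns:

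| Row | Week 64 | Week 76 | EW | FU 2 wk | FU 6 wk |
|---|---|---|---|---|---|
| Hematology | P | x | x | x | x |
| Dispensing | x | – | – | – | – |
| Dosing | x | x | x | – | – |
| PK | – | x | x (fn 7) | – | – |

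The hematology row fills all five cells, so the count is right and the third dosing mark belongs to EW. Appendix 1 has 18 columns. Its dosing row is marked at 2 baselines and at 12 visits from Week 2 to Week 24, so 14 cells. The 18 − 14 = 4 blanks are screening, EW, Week 26 and Week 30. In Appendix 2 the End-of-Treatment dosing cell is also blank.

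**Step 2. Who attends the EW visit?**
- Subjects who have stopped study drug (Section 4.7.1.1; Appendix 10 footnote 2). For them the dosing mark contradicts the text.
- Subjects leaving the study early (Section 4.6.2.3), some of whom may still be taking drug. For them the contradiction is less clear.

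As reproduced, Appendix 9 has no EW column although its footnotes mention the visit, and Section 4.6.2.3 refers only to Appendices 1 and 10. The EW column of Appendix 10 is therefore the only EW schedule shown for the extension.

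**Step 3. Effect on the last-dose date.** Let L be the day of the last regular dose and d the days from then to the EW visit. Without a visit dose, follow-up falls at L + 14 and L + 42, and the adverse-event window closes at L + 42. With a visit dose these become L + d + 14 and L + d + 42. For d = 7 (chosen for illustration) they are 21 and 49 days after the last regular dose. The documents give no distribution of d.

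**Step 4. Timing of the EW PK sample.**

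| Place | Limit on time since last dose |
|---|---|
| Appendix 9 fn 13 | 7 days or less |
| Appendix 10 fn 7 | none |
| Section 4.6.1.8 | none |
| Appendix 1 fn 14 | none |

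Appendix 10 marks the EW sample with a plain x, while its Week 64 laboratory tests carry P for pre-dose. The table therefore does not say whether the EW sample precedes or follows a dose. If d is 2 or more, the last regular dose falls outside the two days for which Section 4.6.1.8 requests dosing times.

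**Step 5. How much could a visit dose contribute to a later sample?** Section 1.2.2.3 puts steady state at about 7 days (168 h). Assume this equals 4 to 5 half-lives: h = 168/5 = 33.6 h to 168/4 = 42 h. The fraction of the steady-state level left after 168 h is then 2^−5 to 2^−4, or 3.1% to 6.3%.

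Assume also one compartment, instant absorption, and an unchanged once-daily dose. The share of the level due to a visit dose given t hours after the last dose is 1/(1 + r), where r = 2^(−t/h) / (1 − 2^(−24/h)).

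| t | h = 33.6 h | h = 42 h |
|---|---|---|
| 24 h | 39% | 33% |
| 48 h | 51% | 42% |
| 168 h | 93% | 84% |

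The visit dose exceeds the residual (r < 1) only after about 46 h to 68 h off drug.

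**The case against.** The strongest reply is that this is one stray table mark. Mandatory stop rules are explicit, footnote 2 sends the reader to Section 4.7.1.1, and no drug is dispensed at EW. The instruction in Section 4.6.2.2 to follow the schedules concerns assessments. A site would have to let the mark override clear text. This stands in part: re-exposure is possible, not certain. But the dosing row is part of the schedule that sites work from, and nothing in the table restricts the mark to subjects still on drug.

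Several stronger readings are tempting and are not supported:

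- **The EW PK sample would reflect the visit dose.** It may be drawn at any time in the visit, and Section 4.6.2.2 places the pre-dose PK sample and safety laboratory draws before the dose. Even for a post-dose draw, step 5 shows that the visit dose does not dominate shortly after the last regular dose. What remains is ambiguity.
- **EW ECG and laboratory results would mix off-drug status with a new dose.** Section 4.6.2.2 puts safety laboratory draws before the dose and, at a shared time, ECG before blood sampling. Appendix 10 specifies no post-dose ECG at EW.
- **Every withdrawal in Weeks 52 to 76 is affected.** Some attendees may still be on drug.
- **The PK footnotes are a serious conflict.** Three of the four places set no limit, so Appendix 9 footnote 13 is the exception and the difference is minor.

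It is also fair to say that a later last-dose date lengthens follow-up, that recorded dose times and diary cards (Section 4.4.2.3) may help, and that the SAP relies little on these data. SAP Section 1 defers open-label data to a separate document, Section 3.2 groups exposure on Week 12 average concentration, and Section 4.5.3 covers exposure and efficacy.

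**Conclusion.** The contradiction is real for subjects who have already stopped study drug: Appendix 10 marks a dose at a visit that its own footnote 2 and Section 4.7.1.1 place after discontinuation, and Appendix 1 marks none. It matters because it is an operative schedule entry in a mainly paediatric trial and because it bears on the date that anchors follow-up. The unclear timing of the EW PK sample is a secondary point.

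The scope is the open-label extension. The number of subjects cannot be derived from the documents. The Week 24 primary comparison and the Week 12 exposure grouping are unaffected. The conclusion rests on the table cells as read from the PDF, whose counts are internally consistent. It does not rest on the half-life assumption in step 5, which only bounds the stronger PK reading. The documents do not settle which dosing instruction was intended, and this review takes no position on it.

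**What to change.** 1. The sponsor should reconcile the EW dosing cell of Appendix 10 with footnote 2 of that table, Section 4.7.1.1 and Appendix 1, so that they give one instruction.
2. State one timing rule for the EW PK sample, including whether any limit on time since last dose applies, and use it in Section 4.6.1.8 and Appendices 1, 9 and 10.
3. Record the date and time of the last dose with the EW sample, whenever that dose was taken.

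The cost is one table cell, aligned wording for the sample rule, and one data field if the last-dose date and time are not already captured with the sample. No visit or procedure is added.

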## **1**                    **BACKGROUND**

This document describes the methods of summarizing and analyzing the data collected in Study BP30153. The main purpose of this document is to describe the data handling rules, derivation rules and statistical analysis methods for the final analysis of the double-blind, 24-week, placebo-controlled period that will be performed by Biostatistics and Statistical Programming and Analysis and that will be reported in the Clinical Study Report. An independent document will be prepared to describe the methods that will be used to summarize the open-label extension (OLE) data. Rules and methods here described will be applied, as appropriate, for any efficacy and safety interim analysis allowed by the study protocol.

Details on the PK and PK/PD analyses performed by the Pharmacometrics group within Clinical Pharmacology may be reported in a document separate from the Clinical Study Report.

This version 2.0 has been developed based on version 1.0, issued on 6-Aug-2018, on study protocol BP30153 version 6, issued on 19-Dec-2018, and on Study File Note “Dose Adjustment Following Review of PK Data by the IMC SOC” issued on 19-Jan-2019.

## **2**                    **STUDY DESIGN**

Study protocol BP30153 version 1-5 were conceived as “A PHASE II MULTI-CENTER, RANDOMIZED, DOUBLE-BLIND, 24-WEEK, **3-ARM, PARALLEL GROUP**, PLACEBO-CONTROLLED STUDY TO INVESTIGATE THE EFFICACY AND SAFETY OF *BALOVAPTAN* (RO5285119) IN CHILDREN AND ADOLESCENTS AGE 5-17 WITH AUTISM SPECTRUM DISORDER (ASD)”, and version 6 as “A PHASE II MULTI-CENTER, RANDOMIZED, DOUBLE-BLIND, 24-WEEK, **PARALLEL GROUP**, PLACEBO-CONTROLLED STUDY TO INVESTIGATE THE EFFICACY AND SAFETY OF *BALOVAPTAN* (RO5285119) IN CHILDREN AND ADOLESCENTS AGE 5-17 WITH AUTISM SPECTRUM DISORDER (ASD)” with recruitment to the balovaptan 4mg equivalent treatment arm closed.

[figure not shown]
The overall study design was built by staggering enrollment by subject’s age, starting first with adolescents (aged 13 to 17 years) and then with children (aged 5 to 12 years). Once the Internal Monitoring Committee (IMC) and the Scientific Oversight Committee (SOC) agreed on acceptable safety and tolerability in the first adolescent cohort (based on data from 8 weeks of treatment, First Study part) and determined the final doses, enrollment of adolescents resumed (for 24 weeks of treatment, Main Study part) and enrollment of a first cohort of younger subjects commenced. Similar process occurred for the first children cohort. See the Study Protocol for more details.

Approximately 340 children and adolescents aged 5 – 17 years with ASD are expected to be recruited to ensure a total of 160 evaluable subjects with placebo or 10 mg equivalent after 24 weeks of treatment.

Subjects who complete the double-blind 24-week treatment period are allowed to participate in an optional 52-week Open-Label Extension (OLE) period where they receive open-label balovaptan treatment (from Week 24 to Week 76).

**For all subjects enrolled prior to protocol version 6**, study design can be visualized as follows:

**Figure 1. Study Design for subjects enrolled up to Version 5**

Doses were initially administered as follows:

**Table 1. Age-adjusted Starting Doses Based on PBPK Model**

| Age (years) | 4 mg eq*  | 10 mg eq* |
|-------------|-----------|-----------|
|             | Dose (mg) | Dose (mg) |
| 5 - 7       | 1.5       | 3         |
| 8 - 11      | 2         | 5         |
| 12 - 14     | 3         | 7         |
| 15- 17      | 4         | 10        |

\*e.q., dose predicted to achieve exposures to 4 mg/day or 10 mg/day, respectively, in adults

During the study, at planned IMC and SOC reviews of accrued data, the starting doses in Table 1 were shown to not achieve the target exposure in children aged between 5 and 14 years. Therefore, new doses were identified to produce exposures equivalent to the 4 mg and 10 mg doses used in adults (Study BP28420) as described by the following Table:

**Table 2. Updated Age-adjusted Doses Based on PK Data**

[figure not shown]
| Age (years) | 4 mg eq
Dose (mg) | 10 mg eq
Dose (mg) |
|-------------|----------------------|-----------------------|
| 5-7*        | 3                    | 7                     |
| 8-17        | 4                    | 10                    |

eq = age adjusted dose equivalent to adult dose; PK = pharmacokinetic.

\* Dose predicted to achieve exposures equivalent to 4 mg/day or 10 mg/day, respectively, in adults

**For subjects enrolled in accordance to protocol version 6,** study design can be visualized as follows:

**Figure 2. Study Design for subjects enrolled in accordance to Version 6**

*eq = equivalent.*

**For subjects randomized in accordance to protocol version 5 but after the 1st of October 2018** the dose is given, once the local IRB approved the plan described in the “Dose Adjustment Following Review of PK Data by the IMC SOC”, at the age-adjusted dose level as described in Table 2.

**For subjects still on-treatment in accordance to protocol version 5 after the 1st of October 2018** the dose is increased, once the local IRB approved the plan described in the “Dose Adjustment Following Review of PK Data by the IMC SOC”, to the age-adjusted dose level as described in Table 2.

The following Table describes the disposition of subjects in relationship with study treatment in the Main study part, 24-weeks period.

**Table 3. Study Treatments in the 24-weeks Main Part (Study Part 2)**

| Age (yrs) | Treatments randomized (1:1:1) according to Protocol Version 1-5 |         |          | Treatments randomized (1:1:1) according to Protocol Version 5 and since 1 st Oct 2018 allowed to start as (*) or to increase to (→) the Adult dose after local IRB approval |           |               | Treatments randomized (1:1) according to Protocol Version 6 |     |          |
|-----------|---|---------|----------|--|-----------|---------------|---|-----|----------|
|           | Plc   | 4 mg eq | 10 mg eq |  | Plc       | 4 mg eq       | 10 mg eq  | Plc | 10 mg eq |
| 5-7       | Plc   | 1.5 mg  | 3 mg     | Treatment started as:  | Plc*      | 3 mg*         | 7 mg*   | Plc | 7 mg     |
|           |   |         |          | Treatment increased to:  | Plc → Plc | 1.5 mg → 3 mg | 3 mg → 7 mg   |     |          |
| 8-12      | Plc   | 2 mg    | 5 mg     | Treatment started as:  | Plc*      | 4 mg*         | 10 mg*  | Plc | 10 mg    |
|           |   |         |          | Treatment increased to:  | Plc → Plc | 2 mg → 4 mg   | 5 mg → 10 mg  |     |          |
| 13-14     | Plc   | 3 mg    | 7 mg     | Treatment started as:  | Plc*      | 4 mg*         | 10 mg*  | Plc | 10 mg    |
|           |   |         |          | Treatment increased to:  | Plc → Plc | 3 mg → 4 mg   | 7 mg → 10 mg  |     |          |
| 15-17     | Plc   | 4 mg    | 10 mg    |  | Plc*      | 4 mg          | 10 mg   | Plc | 10 mg    |

The primary study objective (balovaptan 10 mg equivalent compared to placebo) will be addressed by analyzing the dataset obtained by pooling data from subjects that took placebo or balovaptan 10 mg equivalent, as highlighted in orange in Table 3, and belonging to patterns c) or d), as highlighted in yellow in Table 4 (see Section 4. Statistical Methods for more details).

## **2.1 OBJECTIVES**

### **2.1.1 Primary Objective**

The primary objectives of this study is:

- To evaluate the efficacy of 24-week treatment with balovaptan (RO5285119) 10 mg equivalent compared to placebo as measured by the change from baseline on the Vineland™-II Adaptive Behavior Scales, second edition (Vineland™-II) Two Domain Composite (2DC) (average of Communication and Socialization domains)

### **2.1.2 Secondary Objectives**

The secondary objective of this study are as follows:

- To evaluate the efficacy of treatment with balovaptan 10 mg equivalent vs. placebo on:
  - Change from baseline on the Vineland™-II Composite standard score after 12 weeks and 24 weeks of treatment
  - Change from baseline in the Vineland™-II Communication, Socialization and Daily Living Skills domain standard scores after 12 weeks and 24 weeks of treatment
  - Proportion of subjects with ≥6-point improvement in the Vineland™-II 2DC score (clinically meaningful response)
  - Change from baseline in severity of clinical impressions as measured by CGI-S (Clinical Global Impressions-Severity) and OACIS-S (Ohio Autism Clinical Impressions Scale-Severity) after 12 weeks and 24 weeks of treatment
  - Improvements in clinical impressions as measured by CGI-I (Clinical Global Impressions-Improvement) and OACIS-I (Ohio Autism Clinical Impressions Scale-Improvement) after 12 weeks and 24 weeks of Treatment
  - Change from baseline in patient- or parent-reported Pediatric Quality of Life (PedsQL) v4.0 Generic Core Scale after 12 weeks and 24 weeks of treatment
  - Change from baseline in the Vineland™-II Composite standard score in adolescents and children independently after 12 weeks and 24 weeks of treatment
  - Change from baseline on the Vineland™-II 2DC score after 12 weeks of treatment
- To evaluate safety and tolerability of 24 and up to 76 weeks of treatment with balovaptan
- To evaluate the pharmacokinetics and exposure-response relationships of balovaptan and its metabolites, if appropriate

## **2.2 OUTCOME MEASURES**

### **2.2.1 Primary Efficacy Endpoint**

The primary efficacy endpoint is the change from baseline at Week 24 on the Vineland™-II Adaptive Behavior Scales 2-Domain Composite (2DC) Score, defined as the mean of the Communication domain standard score and the Socialization domain standard score.

### **2.2.2 Secondary Efficacy Endpoints**

The secondary efficacy endpoints are as identified in the list of secondary objectives (see Section 2.1.2)

### **2.2.3 Exploratory Efficacy Endpoints**

Exploratory efficacy endpoints are as follows:

- Change from baseline in behaviors as measured by Aberrant Behavior Checklist (ABC) Lethargy/Social withdrawal subscale after 12 weeks and 24 weeks of treatment
- Change from baseline in repetitive behaviors as measured by Repetitive Behavior Scale-Revised (RBS-R) after 12 weeks and 24 weeks of treatment
- Change from baseline to Week 76 (52 weeks of open-label treatment) as measured by Vineland™-II 2DC score
- Change from Week 24 to Week 76 (52 weeks of open-label treatment) as measured by Vineland™-II 2DC score
- Proportion of subjects with ≥4-point improvement in Vineland™-II 2DC score
- Proportion of subjects with ≥8-point improvement in Vineland™-II 2DC score
- Data (social symptoms, communication, and behavior) from Exit Interviews
- Change from baseline in behaviors as measured by ABC Irritability, Stereotypic Behavior, Hyperactivity/Noncompliance, and Inappropriate Speech subscales after 12 weeks and 24 weeks of treatment
- Change from baseline in patient- or parent-reported PedsQL Cognitive Functioning Scale and parent-reported PedsQL Family Impact Scale after 12 weeks and 24 weeks of treatment
- Change from baseline in caregiver-reported Global Impression (CaGI) severity on communication skills, social skills, daily living skills and overall autism symptoms after 12 weeks and 24 weeks of treatment
- Improvements in caregiver-reported Global Impression (CaGI) impression on communication skills, social skills, daily living skills and overall autism symptoms after 12 weeks and 24 weeks of treatment
- Palatability assessments (taste and acceptability)

